### **10.2. Participants and sample size**

We will invite all young person participants recruited to our feasibility study (n=20) to take part in an individual interview about their experience of BA. We will also seek to recruit up to 7 parents/guardians who have supported their son/daughter when using BA; if more than 7 parents/guardians come forward, we will accept all those interested. Finally, we will recruit up to 10 professionals from a variety of settings, some of whom would have participated in the feasibility study and some who are interested in being trained in BA as part of ComBAT. Our proposed sample sizes are based upon the ones we recruited to co-produce another intervention for an NIHR-funded project, Young SMILES (Gellatly et al, 2019). We will endeavour to capture a wide representation of participants in terms of age, gender, geography and background and, for professionals, roles and services, within the time constraints of the feasibility study.

### **10.3. Recruitment**

### ***Young person recruitment***

All young people recruited to the feasibility study will be asked to attend an individual interview with a ComBAT researcher following their completion of sessions. Interviews will be held following the final session of ComBAT or the last session attended (if a participant withdraws before the end). Consent/assent for young people to take part in interviews will be obtained during their baseline visit with the researcher.

### ***Parent/guardian recruitment***

We will also seek to recruit a sample of parents/guardians to take part in our embedded qualitative study to explore how they have found supporting their son/daughter during BA. How parents/guardians will be recruited and consented to this will be dependent on the age of their son/daughter:

#### *The parents/guardians of young person participants aged 12 to 15 years*

As outlined in section 7.2 all young people entering the research and aged between 12 and 15 years will be required to provide parental consent (alongside their own assent) to be able to participate. This will be obtained during the baseline visit with the research team, during which parents/guardians will be provided with information about the qualitative study. Any parents agreeing to take part in the qualitative study will be asked to complete an additional consent form confirming this during this meeting.

#### *The parents/guardians of young person participants aged 16 to 18 years*

To ensure the representativeness of our parent/guardian sample, we will also seek to recruit some parents/guardians of participants aged 16 to 18 years to take part in the qualitative study. To enable this, any potential participants aged 16 to 18 years (who do not require parental consent to participate in the feasibility study) will be asked whether they would be happy for their parents/guardians to be involved in the qualitative study during their baseline visit with the researcher. If they are happy, we will ask young people to tick a box confirming this on their consent form (see section 7.2) and will provide them with information to pass on to their parents/guardians about the study as well as an expression of interest form. Any parents/guardians interested in taking part will be asked to return their expression of interest form to the research team directly. On receipt of an expression of interest form, the research team will arrange to meet the parent/guardian (online, via telephone or face-to-face), to discuss the research in more detail and obtain consent.

Whilst all interested parents/guardians will be invited to attend a focus group in the first instance, if attendance at an individual interview is preferred or more practical, this will be arranged instead. Information about both interviews and focus groups will be provided to parent/guardians when deciding whether to participate in the qualitative work.

### ***Professional recruitment***

Professionals who delivered BA as part of the feasibility study will be invited to attend a focus group to discuss their experiences of delivering the intervention. If professionals prefer an individual interview rather than attend a focus group, we will arrange an interview instead. Apart from the professionals who participated in the feasibility study, we will also invite professionals who are interested in joining the ComBAT research programme, as well as their managers, to participate in further focus groups. Information about the qualitative study and an expression of interest form will be emailed to these professionals via the relevant gatekeeper from a variety of

services including the NHS, schools and the third sector. Potential participants will be invited to return an expression of interest form or contact the study team directly if they are interested in taking part or need further information. As part of their expression of interest, professionals will note whether they prefer to join a discussion group or have an individual interview.

#### **10.4. Procedure**

We will ask parents/guardians who are interested in participating to complete three introductory questions about their sex, age and relationship with the young people. Professionals will complete a brief questionnaire that asks their sex, age, professional role, service they work with, and whether they have delivered BA previously.

Focus groups and interviews will be held online using a video conferencing platform approved by the study sponsor. To accommodate the needs of all participants, the option to attend an interview face-to-face or via telephone will be offered in place of video conferencing if preferred or more practical. Any interviews conducted face-to-face will be completed in a mutually convenient location. If several participants per sample would prefer to attend a focus group face-to-face these will be held in a suitable space within the recruiting site.

All focus groups and interviews will follow a structured topic guide. Focus groups (with professionals and parents) will last up to 90 minutes and interviews (with young people and parents/professionals if requested) will last up to 30 minutes. The topic guides include how we can tailor the BA intervention to meet the needs and preferences of young people, how we can successfully incorporate parental support into the intervention and how we may overcome the barriers of engaging young people with mild to moderate depression to complete BA. We will ask professionals about the best methods of providing clinical supervision to ensure the safe delivery of BA and what costs are associated with care for depression in the NHS and in non-NHS organisations, as well as costs incurred by young people and their families.

All interviews and focus groups will be audio recorded and transcribed verbatim, to which participants would have given permission when signing the consent form. They will be reminded that the discussion will be recorded before it starts. All study materials (i.e. demographic questionnaires, transcripts) will each be given an individual identifier as to maintain participant confidentiality.

Participants will be reminded of their right to withdraw before the interview or focus group. However, any data collected at the point of withdrawal will be included in the analysis as agreed during the consent process.

#### **10.5. Data analysis**

All interview and focus group transcripts will be analysed using a template analysis because this allows for both deductive and inductive coding. The deductive coding will be guided by the items on the Intervention Taxonomy (ITAX; Schulz et al., 2010); a classification system which can be used to describe the main characteristics of an intervention. The ITAX comprises two tables, the first of which outlines characteristics associated with intervention delivery (e.g. delivery mode, materials, location) whilst the second describes content and goals (e.g. delivery strategies, processes). Inductive coding will produce *de novo* themes emerging from the narrative data. Two researchers (who will have received training in template analysis) will carry out independent coding. The two coders will have regular meetings to ensure that the emerging codes remain grounded in the original data.

We will hold 2 synthesis workshops with our 2 PPI advisory groups (one with young people and one with adults – parents/guardians and professionals) where we will present the final coding framework and example quotes (anonymised) to arrive at a provisional content and delivery details for our proposed BA intervention. Following the 2 synthesis workshops, we will make iterative changes to our coding framework and produce the following resources: a session-by-session guide for mental health support workers, materials for young people and their parents to use at home, and a “training the trainers” package for specialists who will teach and supervise BA.

## **10.6. Ethical considerations**

Although this qualitative work seeks to obtain information about the development of an intervention and does not seek to explore personal experiences in depth, several ethical considerations are required.

Firstly, during interviews and focus groups some participants may choose to discuss sensitive topics which they, or others may find upsetting. In the event of a participant becoming distressed, several measures may be taken depending on whether this occurs during an interview or focus group discussion. If a person becomes distressed during an interview, the interviewer will offer to pause the interview and recording and suggest taking a break. Following a break, the option to continue the interview will be offered as well as the option to postpone or, if required, cease their involvement in the study. If a person feels like they require additional support, the researcher will arrange this and liaise with the relevant professionals (e.g. CAMHS clinicians, ComBAT chief investigator and co-applicants trained in supporting distressed individuals). This will be explained to all participants in the participant information sheet and reiterated prior to the interview start.

If a person becomes distressed during a focus group, the facilitator will offer to pause the discussion and recording and suggest taking a break or will ask the participant whether they would like to temporarily leave the discussion. The facilitator will determine the best approach to be taken on a case-by-case basis. Outside of the discussion (either in person or via video conferencing as appropriate) the participant will be given the option to re-enter the discussion, arrange an interview at a different time for them to complete their involvement or, if required, cease their involvement in the study. If a person feels like they require additional support, the researcher will arrange this and liaise with the relevant professionals (e.g. CAMHS clinicians, ComBAT chief investigator and co-applicants trained in supporting distressed individuals). This will be explained to all participants in the participant information sheet and reiterated prior to focus group start.

All researchers conducting interviews and facilitating focus groups have experience of supporting people in distress and will receive additional training to enable them to enact these measures if they feel it necessary. Following all interviews and focus groups all participants will be provided with information about services that they are able to contact for additional support if required.

Confidentiality of participants and the data obtained will be maintained throughout. All data obtained from participants will be assigned an identifier with no personal information collected and pseudonyms will be used when reporting all results. All recordings will be made using encrypted devices with recordings deleted immediately following transcription. We will also ensure that ground rules are set prior to all interviews and focus groups whereby we will ask participants to refrain from disclosing any personal or family information. We will follow a structured topic guide and keep discussions focused on the research objectives. All group facilitators will have a health, social care or educational background and relevant DBS checks.

- **13. EMBEDDED PROFESSIONALS' SURVEY**

**11.1. Study design**

Alongside the feasibility study we will conduct a short survey to find out what path young people with mild to moderate depression may take to access help in different settings and locations. The survey questions are based on the ITAX (Schulz et al., 2010, see section 10.5). All survey questions will be interpreted with flexibility for 'usual care' which may not involve a specific intervention, but rather a less directive and less defined process of support.

**11.2. Participants and recruitment**

Professionals working with young people experiencing mild to moderate depression and based within local and specialist CAMHS, mainstream and special schools, improving access to psychological therapies (IAPT) services, voluntary agencies for young people, community paediatrics, residential social care settings, and other specialist local authority services will be invited to complete the survey. A link will be distributed to whole teams via secretaries with all professionals asked to share the link with other, relevant colleagues.

**11.3. Procedure**

The survey will be hosted on the Qualtrics Platform with individuals able to complete it online or via telephone with a member of the research team, depending on preference. If any individuals/sites express that they would be happy to elaborate on their survey answers or they would like to find out more about the research, a telephone or face-to-face conversation will be arranged. The survey has been designed to be brief and take approximately 10 minutes to complete.

To complete the survey all professionals will need to agree to a consent statement. This reiterates the study aims, explains data storage arrangements and provides important information about principles of General Data Protection Regulation (GDPR).

The survey comprises a combination of short answer questions with drop-down boxes embedded (where possible) for ease of completion. Survey questions explore the services to which participants belong, the treatments (if applicable) offered to young people (including their duration, session number and length), the professionals responsible for delivering interventions to young people, any thresholds in place for service acceptance, how young people reach services (i.e. self-referral, GP referral) and whether services signpost young people with mild to moderate depression elsewhere. No personal information is collected as part of the survey with all responses being anonymous. However, if a participant wishes to arrange a further follow-up call to discuss the study or their responses in further detail, they will be required to provide their contact details. All participants will be informed of their right to withdraw as part of the consent statement, however any data obtained prior to withdrawal will be retained as agreed when consenting to participate.

Two fortnightly automated reminders will be sent to the professionals to encourage survey completion.

**11.4. Sample size**

We will recruit professionals until we reach data saturation, i.e. where we feel additional data collection does not add substantially to the findings. The responses to the survey questionnaire

will be reviewed weekly in order to ascertain this. If the response rate is poor, we will contact key individuals (e.g. the CCG and local authority commissioners) to facilitate communications with their local NHS and non-NHS agencies and organisations.

### **11.5. Data analysis**

All survey responses will be analysed by themes using the ITAX (Schulz et al., 2010). This will produce a roadmap of the different “journeys” that young people with depression may take in order to access evidence-based interventions across different sites. This information will be used for two purposes. First, to understand what ‘usual care’ options we are likely to encounter in our subsequent RCT. Particularly, it is important for us to identify sites where usual care includes BA, or sites where no support is in place for young people randomised to usual care. Second, the roadmap will help us plan different delivery models for our BA intervention that fit different types of usual care. We need to ensure that the ComBAT research is provided in schools and the third sector in a way that fits, as much as possible, with existing and evolving ways of working.

## **14. MONITORING, AUDIT AND INSPECTION**

Throughout completion of the feasibility study, as well as the subsequent RCT, trial monitoring and site monitoring procedures will be followed in accordance with the standard operating procedures of both the study trials unit (York Trials Unit) and the study sponsor (TEWV). The conduct of the study will be governed by a Programme Steering Committee (PSC) which has been established as part of the wider 5-year ComBAT research programme. This committee comprises an independent chair, two independent senior academics, two representative of young service users and two parents/carers. The PSC will meet once a year and will monitor progress, protocol adherence and will provide advice to the Chief Investigator, the NIHR, the University of York and TEWV. All resources produced from the findings of the feasibility study will be presented to the PSC ahead of testing in the larger RCT.

## **15. ETHICAL AND REGULATORY CONSIDERATIONS**

### **13.1. Health Research Authority (HRA) review**

Ethical approval in line with NHS Research Ethics Committee (REC) and HRA guidance will be sought for the completion of this feasibility study. Both the REC and HRA will be notified of, and asked to review, any proposed changes to the procedures and/or study documentation made during the study. As no pharmaceutical compounds or medical devices will be used in the study Clinical Trials Authorisation will not be required.

### **13.2. Ethical considerations**

Several ethical issues have been considered to enable the safe running of this feasibility study. First, young people with depression can be vulnerable and may experience distress or worsening symptoms during their participation. All participants entering the study will be provided with information outlining who to contact if they (or their parent/guardian, if applicable) have any concerns or worsening symptoms during participation. This will include providing individuals with the contact information of their local CAMHS duty clinician service which provides urgent assessments during office hours on weekdays. In the event that a participant feels at risk outside of these hours they will be signposted to the out of hours on-call service provided by consultant psychiatrists which is available 24 hours a day, 7-days per week. In serious situations young people will be directed to present at their local A&E department or call 999. This will be made

clear within the participant information sheets and reiterated during the visit (baseline) with the researcher. Agreement to seek additional support if required will be a requisite of study entry.

During any contact with the research team, if we consider a young person to be at risk we will ask the parent/guardian, and the young person, for permission to liaise with the relevant support services (e.g. social care/child protection/mental health). If the level of risk warrants it, the research team will directly contact the relevant services, having obtained informed consent from the participants before they entered the project (the consent form will state “risk” as a criterion for breaching confidentiality). During their participation, all young people will have access to usual care with this communicated to them clearly. If a professional delivering BA feels that the complexity or severity of the depression or other problems warrants more high-intensity treatment, they may decide to discontinue the participant from the research.

Throughout the research, any adverse events (e.g. distress, misunderstandings, deteriorating mental state) will be monitored closely by the research team. We will encourage all participants to speak to their support workers if they are unhappy about their participation in the research. We will explicitly state in the study information sheet that participants can withdraw from the project at any time and do not have to give a reason. Withdrawal from the research will not impact upon any therapies they may receive now or in the future.

All data collected from participants during the feasibility study will be confidential and will not contain any information that may lead to the identification of an individual. All participants will be assigned with an ID number which will be used on any questionnaires they complete. All ID numbers will be randomly generated and not be based upon any participant identifiable information. All information will be stored securely and adhere to GDPR regulations and the principles of the Data Protection Act (2018) (see section 3 for more information about data storage).

Finally, as some participants may prefer for their baseline and follow-up assessments to be conducted face-to-face, we will adhere to the University of York’s lone worker policy in these instances. This will be adhered to if visits are conducted in non-public locations (e.g. participant homes). This will include enacting a ‘buddy system’ whereby any researcher conducting a face-to-face visit will inform colleagues of their location, appointment times and expected end time. All researchers will ensure that they inform a colleague of their arrival at a visit and also at their departure.

We acknowledge that taking part in this feasibility study will require young person participants to attend treatment sessions over a period of up to 8 weeks, complete a series of outcome measures at baseline and follow-up and attend an interview about their experiences. As a thank you, all young person participants will receive a £25 Love to Shop voucher following their interview in recognition of their contribution.

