## 5. OBJECTIVES AND OUTCOME MEASURES/ENDPOINTS

### 3.1. Aims and Objectives

This study is part of a larger, 5-year programme of research called ComBAT. The current study is the first of several work packages which will be completed as part of ComBAT and aims to adapt and standardise BA to be delivered by mental health support workers in community settings, such as schools and youth centres.

To ensure that new interventions are developed to accommodate the needs and preferences of their target users, co-production is increasingly used within this context (Jones et al., 2020; Boyd et al., 2012). This approach recognises the importance of collaborating with important stakeholder groups and end users when developing interventions to increase the likelihood of them being considered useful, engaging and satisfying (Thabrew et al., 2018). This initial work package focuses upon co-production and road mapping and seeks to involve a range of stakeholders to evaluate the first version of the new BA intervention. The information provided will be used to refine the intervention ahead of testing in a full-scale RCT.

A single-group pre-post feasibility study, with an embedded qualitative study and a parallel professional survey, have six objectives:

1. Produce a suite of standardised ComBAT resources, including:
  - a. a session-by-session guide for professionals who deliver the BA intervention
  - b. materials for young people and their parents who use the BA intervention
  - c. a “training the trainers” package for specialists who teach and supervise the BA intervention
2. Map what “usual care” means - and plan the potential delivery models for the BA intervention (who, when, where and how) that fit usual care - across the range of community settings where young people may seek support for depression.
3. Road-test the BA intervention resources and arrive at a final iteration of the intervention and a protocol for its at-scale delivery.
4. Develop the Resource Utilisation Questionnaires for Adolescents (RUQ-A).
5. Measure intervention uptake, adherence, completion of follow-up measures and data missingness in the questionnaires.
6. Capture the experiences of young people and parents who participated in the intervention and of professionals who supported them.

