### **7.3. Procedure**

Following informed consent/assent the young person participant will complete a series of standardised questionnaires with a trained researcher. These will include a demographic questionnaire, RCADS, CDRS-R, BADS-SF, CHU-9D and RUQ-A (for questionnaire description see section 3.2). On completion of the baseline measures, participants will be offered the BA intervention. Treatment sessions will be arranged by the supporting professional who will liaise with the young person and, if appropriate, their parent/guardian. The researcher will arrange a follow-up session at 8 weeks from baseline and will keep in contact with the young people before the 8 weeks as needed.

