### 9.2. Data analysis

We will tabulate the demographic information and data on each outcome measure at baseline and post-treatment for each participant (like a case series). We will also describe the data collected from the RUQ-A to identify the main costs associated with depression for NHS and non-NHS organisations and to assess whether the tool needs to be revised to inform data collection methods in a future trial. As this is a feasibility study, we will not conduct any statistical analysis or use the outcome data as a measure of effect.

For our primary outcome measure (RCADS brief version), we will present raw and T-scores for each participant on the depression and anxiety sub-scales and in total. We will also indicate, based on the established clinical cut-offs, in which severity group participants belonged at baseline and post-intervention (clinical, sub-clinical and non-clinical). For our main secondary outcome, the CDRS-R, we will present both the continuous scores and the categories according

to the scale's cut-off scores (no depression, emerging or early depression, diagnosable depression).

We will report intervention uptake (percentage of those eligible who consented to the study), adherence (session attendance and number of participants who withdraw and the reasons for withdrawal), completion of follow-up measures (number of participants who completed the questionnaires at 8 weeks from baseline including those who did not adhere to the intervention) and data missingness in the questionnaires (number of items missing and which items received no responses).

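### The rule letting the BA professional discontinue a participant from the research, rather than from BA, can end the 8-week follow-up and interview that the plan otherwise keeps for early stoppers

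*Protocol*

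**What the plan says.** Section 13.2 (Ethical considerations) gives the professional delivering BA a discretionary power. If that professional judges that "the complexity or severity of the depression or other problems warrants more high-intensity treatment", then "they may decide to discontinue the participant from the research".

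Later in the same section, participants are reassured about leaving: "Withdrawal from the research will not impact upon any therapies they may receive now or in the future". Its closing paragraph describes what taking part involves: attending treatment sessions, and also to "complete a series of outcome measures at baseline and follow-up and attend an interview about their experiences".

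Other sections deal with follow-up and early stopping:

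- Section 3.1, objective 5: "Measure intervention uptake, adherence, completion of follow-up measures and data missingness in the questionnaires".
- Section 7.3 (Procedure): the supporting professional arranges the treatment sessions, whereas "The researcher will arrange a follow-up session at 8 weeks from baseline".
- Section 9.2 (Data analysis): completion of the 8-week questionnaires is counted "including those who did not adhere to the intervention".
- Section 10.3 (Young person recruitment): the interview takes place after the final session or after "the last session attended (if a participant withdraws before the end".

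**The concern.** Stopping a treatment and stopping data collection are separate decisions. The clinical reason in section 13.2, that a young person needs something more intensive, justifies the first but does not by itself require the second. The sentence is nevertheless written in terms of the research and not of BA, so a site following it could reasonably cancel the follow-up visit and the interview together with the sessions.

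Any loss would not be random. The trigger is severity or complexity, so the missing 8-week rows and interviews would belong to those for whom BA in a school, third-sector or CAMHS setting was judged not enough. Their experience bears directly on refining the intervention before the randomised trial, after which section 6 (Study design) says it can no longer be changed. Objective 5 (follow-up completion and missingness) and objective 6 (participants' experiences) are the two affected. Part of any shortfall in completion would then come from the protocol's own instruction and not from participants' willingness or ability to be followed up.

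**Working it through.** No arithmetic applies. The protocol states no discontinuation rate, and the concern disputes none of its figures. The check is a comparison of the text.

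**1. What the research means in section 13.2.** The reassurance about withdrawal treats the research as something a participant can leave without affecting therapy, so research and care are kept apart. The closing paragraph lists sessions, baseline and follow-up measures, and an interview as the content of taking part. On that usage, being discontinued from the research ends all of these. Narrower wording was available: section 9.2 speaks of adherence to the intervention when it means BA alone.

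**2. How the plan treats people who stop BA early.**

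| Item | Section | Treatment of early stoppers |
|---|---|---|
| 8-week visit | 7.3 | Arranged by the researcher for the participant; not tied to attendance at sessions |
| 8-week completion | 9.2 | Counted with non-adherers included |
| Interview | 10.3 | Held after the last session attended if the participant withdraws early |

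All three point towards keeping early stoppers under observation.

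**3. Whether these rules reach a professional-led discontinuation.** Section 9.2 refers to participants who withdraw and to non-adherers. Section 10.3 refers to a participant who withdraws. Neither names a participant whom the professional has discontinued, and section 7.3 gives no rule for that case. No section says that the measures or the interview continue afterwards.

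**4. Two readings remain.**

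- *Sessions only.* The professional arranges only the sessions (7.3), so the power may extend no further. Section 13.2 then agrees with 7.3, 9.2 and 10.3, but its wording is loose.
- *Whole study.* This is the ordinary sense of the words and fits the usage in step 1. Follow-up and interview then end for this group, against the direction of step 2.

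The text does not choose between them, so this is an ambiguity and not a strict contradiction.

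**5. What follows on the whole-study reading.** Discontinued participants would have empty 8-week entries in the per-participant table planned in section 9.2. They would count against follow-up completion and would give no interview. Three things would not change: no effect estimate is planned (9.2), deterioration is still monitored as an adverse event (13.2), and withdrawals are reported with reasons (9.2).

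**The case against.** The strongest reply is that the operational sections already settle the matter. Section 9.2 handles withdrawal under adherence and still seeks questionnaires from non-adherers. Section 10.3 interviews participants who withdraw. Section 7.3 gives the professional no say over the researcher's assessment. Section 13.2 is a safety paragraph and should be read in that light, and its reassurance about withdrawal concerns the participant's own decision, not the professional's.

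A second line is that even the whole-study reading is defensible. Section 6.2 excludes young people eligible for high-intensity CAMHS care, and section 13.2 applies the same boundary after entry. Sparing a deteriorating adolescent another set of measures is a reasonable ethical judgement.

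A third is that nothing reported would mislead. There is no effect estimate, the per-participant tables would show the gap, and a participant stepped up and lost to follow-up is itself a feasibility result.

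Much of this stands as a limit on importance. The sessions-only reading is possible, the rule is permissive, and no estimate is biased. It does not remove the point. The sections relied on do not name professional-led discontinuation, and the one sentence that does uses the wider term. The ethical argument supports letting the young person decline follow-up; it does not support having the professional's decision end it without an offer. A gap that is visible and explained is still information lost, here from a group of particular interest to a study meant to refine the intervention.

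**Conclusion.** The concern holds, as a minor point. Section 13.2 is ambiguous, and in its ordinary sense it allows avoidable loss of 8-week data and interviews among participants selected on severity or complexity.

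No size is claimed. The conclusion assumes that at least one participant is discontinued under the rule and that the site reads it as covering the whole study; the protocol gives no basis for judging how likely either is. The consequence is confined to follow-up completion, missingness, the per-participant outcome tables and the interview sample. If the sponsor meant sessions only, the intention is sound and only the wording needs correcting.

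**What to change.** In section 13.2, replace the discontinuation clause with wording such as: the professional may discontinue the BA intervention and arrange step-up to more intensive care; the participant is still offered the 8-week measures, the interview and adverse-event follow-up unless the young person or parent withdraws consent.

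The clinical decision about who stops BA, and when, stays as written, and the participant remains free to decline. Agreement to the interview is already obtained at the baseline visit (section 10.3), and the researcher already arranges the 8-week session (section 7.3), so no new procedure is needed. The cost is one sentence, plus some research contact with young people who are by then in other care.
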